5.5 Last study visit

At 6 months, follow-up will be achieved by telephone by the Coordinating Centre.

- At 90- and 180-day data:
 - a. Vital status
 - b. Location: still ICU (or date discharge), hospital ward (or date discharge), rehabilitation centre, long-term facility, home (date discharge to home)
 - c. co-interventions: mechanical ventilation (or date weaned off), renal replacement (or date weaned off), vasopressors (or date weaned off)
 - d. core temperature (lowest and highest of the day), vital signs (lowest and highest values for heart rate, systolic and diastolic blood pressure) if still at hospital
 - e. Glasgow coma scale Cognitive function
 - f. MDRS score
 - g. HRQoL, promis

5.6 Early termination visit

Patients are allowed to withdraw their participation in the research at any time and for any reason. Patients included in the research (unable to consent or included by a relative) can refuse to continue their

participation after recovery.

The investigator can temporarily or permanently withdraw a participant from the study for any safety reason

or if it is in the participant's best interests.

If a participant wishes to withdraw their consent from the study, we will use the following strategies to minimize the impact on the validity of the trial meanwhile respecting the participant's right to withdraw. We will seek a better understanding of the patient's wishes and offer the following alternatives to complete withdrawal:

1) Discontinue in-person follow-up but allow telephone follow-up;

2) Discontinue in person and by telephone follow-up but allow access to medical records and to use personal data to be able to get life status from the national centre of epidemiology of deaths (Centre d'épidémiologie sur les causes de décés - Cépidc) via the SNDS (Système National des Données de Santé).

In any case, all the data that would have been collected before the patient's consent withdrawal will be kept in.

5.7 Expected length of participation and description of the chronology and duration of the study.

- Duration of enrolment period: 48 months

- Duration of participation for each participant: 6 months
 - o Treatment period:7 days

- o Duration of follow-up period:6 months
- Total study duration: 54 months
- Randomization (Interventional phase): will be performed after the inclusion visit, less than 24 hours after receiving the results of the biomarker.
- Follow-up duration and procedures for the participant in the event of premature discontinuation

5.8 Table or diagram summarising the chronology of the study

							Da	ays						6 months
	0	1	2	3	4	5- 6	7	8- 9	10	11- 13	14	28	90	
Verification of inclusion and exclusion criteria	X													
Informed consent	Х													
Source of infection		х												
Severity of illness (SAPS II score)		x												
Sepsis data		х												
Pre-existing comorbidities (Charlson comorbidity index, Clinical Frailty Score)		x												
Randomization* (Interventional phase)		х												
Dispensation of treatments		X	X	Х	X	Х	Х							
Biological samples<	Х	Х	x	х	х	х	х	х	x	х	х	x		
Additional Biological samples (biomarqueurs)	X	Xa					X							
Protocol adherence ^b		х	Х	Х	Х	Х	Х							
Co-interventions ^c		Х	Х	х	х	Х	х	Х	х	х	Х	Х	х	
Death or persistent organ dysfunction ^d		х	x	x	х	х	x	х	х	х	x	х	х	x
Vasopressor dependency		х	x	x	х	х	x	х	х	х	x	Х	х	
Organ function including renal function (SOFA score)*	Х	x	x	X	X		X		x		X	x		
HRQoL (EQ-5D-5L) ^e , Promis		x										х	х	x
Serious adverse events*		x	Х	Х	Х	х	x	х	х	х	х	х	x	X

^aMust be collected before the first dose of investigational product. Samples include blood, urine, cells, exhaled air

^bReceipt of every planned dose according to schedule until completion of 7-day treatment protocol, samples collected per protocol instructions, biomarkers collected before the first dose of investigational product.

^cAdministration of mechanical ventilation, renal replacement, vasopressors, vitamin C, thiamine, intravenous fluids, blood products, sedatives, and antimicrobials. Daily data until ICU discharge or 28 days (whichever comes first).

^dDependency on mechanical ventilation, renal replacement, or vasopressors. eEQ5D to be filled at 3 and 6 months

* Interventional trial

5.9 Distinction between standard care and study

TABLE: "Standard care" vs. "additional interventions" required specifically for the study

Interventions, procedures and treatments carried out for	Interventions, procedures and treatments associated	Interventions, procedures and treatments added for
research purposes	with standard care	research purposes
Verification of inclusion and		X
exclusion criteria		
Informed consent		X
Source of infection	Х	
Severity of illness	Х	
(SAPS II score)		
Sepsis data	X	
Pre-existing comorbidities	Х	X
(Charlson comorbidity index, Clinical		
Frailty Score)		
Randomization		X
Dispensation of treatments	Х	Х
Biological samples	Х	X
Additional Biological samples		X
Protocol adherence ^b		X
Death or persistent organ		X
dysfunction ^d		
Vasopressor dependency	X	X
Organ function including renal	Х	X
function (SOFA score)		
HRQoL (EQ-5D-5L)		X
Serious adverse events		X

5.10 Biological samples collection

Samples (serum, DNA, urine, ...) taken as part of the study will be stored in a biological sample collection.

During the study the sample collection(s) will be stored at the laboratory of Centre de Ressources Biologiques (CRB) Paris Saclay, under the supervision of Pr [name] / [name] [name]) for a period of 30 years . Relevance of the collection/purpose *(see table below)*

At the end of the study, the samples will be stored.

At the end of the study, the samples may be used for further analysis not described in the initial protocol but which may be useful for investigation of the condition **sepsis** /in light of advances in scientific knowledge, provided the participant is informed and does not oppose this, as stated in the information note/consent form.

The sample collection will be declared to the ministry of research [and to the director of the competent regional healthcare authority - **amend as necessary** if the entity is a health establishment (Article L. 1243-3 of the *Code de la Santé Publique* [French Public Health Code]).

Type of	Quantity	Storage	rench Public Hea Supervisor of		Storage	End
sample		location (name and entity)	the sample collection (name and entity)	of the sample collection	duration	use/Future (e.g. destruction)
Serum Tubes	3X3.5 mIX3 (Day 0, Day1 and Day7)	GH PSO	Pr [name] / Mme [name] Centre de Ressources Biologiques (CRB) Paris Saclay	biomarke rs	30 years	destruction
EDTA tubes	2X 6ml X3 (Day 0, Day1 and Day7)	GH PSO	Pr [name] / Mme [name] Centre de Ressources Biologiques (CRB) Paris Saclay	bio markers	30 years	destru ction
Paxe gene Blood	1X 10 ml X3 (Day 0, Day1 and Day7)	GH PSO	Pr [name] / Mme [name] Centre de Ressources Biologiques (CRB) Paris Saclay	biomarke rs	30 years	destruction
Mono vette Urine	1X 10 mIX3 (Day 0, Day1 and Day7)	GH PSO	Pr [name] / Mme [name] Centre de Ressources Biologiques (CRB) Paris Saclay	biomarke rs	30 years	destruction

5.11 The investigational medicinal products

5.11.1 Description of the drugs :

- Hydrocortisone hemisuccinate / placebo:

Vials with 100 mg hydrocortisone or placebo lyophilisate for IV injection; provided by SERB laboratory, [name].

Store at room temperature.

Water for injection needed for the reconstitution for IV injection of hydrocortisone/placebo will not be specifically provided by the Sponsor but taken from hospital stocks (all available presentations) and reimbursed as additional costs

- Fludrocortisone / placebo:

Tablets of 50 µg or placebo; provided by HAC Pharma laboratory, [name].

Store at room temperature

5.11.2 Presentation of patient boxes :

Treatments will be presented in numbered boxes, labelled for this study according to the Good Manufacturing Practices under the responsibility of the Clinical Trial Department of AGEPS (Agence Générale des Equipements et Produits de Santé).

Each numbered box will contain all corticosteroids or placebo necessary for a full treatment for each patient, identified by a specific number:

- 30 vials of hydrocortisone 100mg / placebo (2 extra vials)
- 1 blister of 10 tablets of fludrocortisone 50 µg / placebo (3 extra tablets)

5.11.3 SUPPLY OF THE INVESTIGATIONAL CENTERS

The shipments to the hospital pharmacies will be insured by the the Clinical Trial Department of AGEPS.

Supply:

Numbered boxes will be sent after the opening visit.

Re supply:

Re-supplies of patient boxes will be ordered via the eCRF : boxes will be automatically sent to the centers' pharmacies according to their remaining stock.

The hospital pharmacist (with respect to domestic procedures) will confirm receipt in writing of all batches of the study medications and maintain an accurate accounting of them.

Storage:

Treatments have to be stored in a secured local.

Dispensing:

Pharmacies will dispense boxes to the care unit on the basis of a specific prescription edited by the investigator from the eCRF. The traceability will be insure with the peel-off label present on each and affixed on the prescription.

Dispensing corticosteroids/placebo kits is performed only once.In case of anomaly (broken vial), a new prescription will be edited via the eCRF, and another box may be dispensed.

Accountability and destruction:

These will be organized by the CRA through the study. After completion of the study, all drugs boxes (unused, returned...) must be returned to CTD-AGEPS for a central destruction.

5.11.4 POSOLOGY AND DRUGS ADMINISTRATION

Initiation of treatments:

Treatment should be started immediately after randomization (day 0 of the study).

Posology:

- Hydrocortisone hemisuccinate /placebo will be given as 50 mg intravenous bolus every 6 hours

- Fludrocortisone /placebo* will be given as a 50 µg tablet via a nasogastric tube once per day in the morning

* Patients with COVID-19 will receive only experimental fludrocortisone or its placebo AND NOT hydrocortisone or its placebo as they will receive dexamethasone as the standard of care.

Duration of treatments:

Study drugs will be given until the patient will be discharge from the ICU for a maximal treatment duration of 7 days for steroids. Study drugs will be stopped without tapering off.

Reconstitution for IV injection of hydrocortisone/placebo:

Hydrocortisone hemisuccinate lyophilisate will be reconstituted prior to use with 2 mL water for injection. The solvent must be injected gently into the vial. Reconstitution and dilution should be performed in accordance with Good Clinical Practices guidelines, particularly with respect to asepsis and to Hydrocortisone SmPC. Hydrocortisone must not be used if the reconstituted solution has a cloudy appearance or contains floccular or particulate matter. The SmPC instructions for use, handling and disposal should be strictly followed.

The volume injected will be 1 mL, containing 50 mg of Hydrocortisone.

"Administration of fludrocortisone/placebo

A 50 μ g fludrocortisone/Placebo tablet is administered, enterally, once a day. For patients with a nasogastric tube, the entire tablet will be introduced into the nozzle of the tube. The tube will be flushed with 50 mL of water (the 10 first mL have to be injected slowly) and clamped for at least 30 minutes after tablet administration."

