2 STUDY OBJECTIVES

The overall objective of the study programme is to determine whether different signatures of immune status and/or corticosteroids biological activity influence the responses to hydrocortisone plus fludrocortisone of adults with sepsis. To this end, several predefined biomarker cohorts of patients will be randomly allocated to receive hydrocortisone plus fludrocortisone or their respective placebos with "primary objective" and "secondary oobjectives" defined below.

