2.1 PRIMARY OBJECTIVES OF EACH ANALYSIS BY BIOLOGICAL MARKER

To compare the effect hydrocortisone plus fludrocortisone vs. placebo on a composite of death or persistent organ dysfunction – defined as continued dependency on mechanical ventilation, new renal replacement therapy, or vasopressors – assessed at 90 days on intensive care unit (ICU) adults and having different biological profiles for immune responses and corticosteroids bioactivity.

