4.1.2 Exclusion Criteria (interventional phase)

1) Pregnancy;

- 2) Expected death or withdrawal of life-sustaining treatments within 48 hours;
- 3) Previously enrolled in this study;
- 4) Formal indication for corticosteroids according to most recent international guidelines
- 5) Vaccination with live virus within past 6 months
- 6) Hypersensitivity to hydrocortisone or fludrocortisone or any of their excipients (SPC)
- 7) Women of childbearing potential not using contraception
- 8) Nursing women

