5) **Endotype B cohort**: as defined by endotyping of 100 genes reflecting adaptive immunitiy and glucocorticoid receptor signalling. This approach in children with sepsis identified two distinct endotypes A and B. Endotype A was characterized by repression of the majority of these genes (Wong 2011).

Patients presenting with an endotype A have a profile of immune suppression, and were at higher risk for mortality. Nevertheless, those patients with an endotype A at ICU day 1 that shifted for an endotype B later on draw benefit from corticosteroids (Wong 2018).

6) *PCR COVID-19 cohort*: the emergence in the end of 2019, of a novel coronavirus, SARS-CoV-2, related disease, places a major burden on worll health care systems. The disease is characterized by viral sepsis with a key role of over-activation of the complement system and inflammatory mediators. Corticosteroids have been provent to reduce mortality at 28-day (RECOVERY 2020; Sterne 2020) The phenotype COVID-19 may identify among patients with sepsis those who may be benefit from corticosteroids. In this biomarker cohort, all patients will receive dexamethasone 6 mg per day for 10 days and will be assigned to fludrocortisone or its placebo. Indeed, dexamethasone has no mineralocorticoid activity. The added value of mineralocorticoid is worth being evaluated owing to the role of angiotensin-converting enzyme 2 receptor and endothelial dysfunction in the pathogenesis of COVID-19.

7) **PCR Influenza cohort**: seasonal influenza causes yearly thousands of death primarily by pneumonia related sepsis. While retrospective observational studies reported controversial effects of corticosteroids in these patients, there are still no high quality randomized trial to inform routine practice.

8) *PCR other respiratory viruses cohort*: likewise, seasonal non-influenza viral pneumonia causes thousands of death due to sepsis. While retrospective observational studies reported controversial effects of corticosteroids in these patients, there are still no high quality randomized trial to inform routine practice.

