9 STATISTICAL ANALYSIS

9.1 SAMPLE SIZE DETERMINATION

We will enroll a total of at most 1800 patients. Sites are expected to enroll at least 1 or 2 patients per month.

Adaptive outcomes

The goal is to develop an adaptive clinical trial design which evaluates the therapeutic intervention of targeted therapy, identifies subset of subjects who respond better to the experimental therapy.

Sequential analyses will use the number of vasopressor-free days at day 28 as the measure of efficacy, and the occurrence of severe adverse events within the first 28 days as the measure of toxicity. According to the literature (the APPROCCHS trial), the number of vasopressor-free days at day 28 in the hydrocortisone+fludrocortisone group was 17.1 ± 10.8 versus 15.0 ± 11.1 in the placebo group. Thus, a sample of 176x2=352 patients achieves 80.04 % power to reject the null hypothesis of equal means when the mean difference between arms is 3 days with SD of 10 days, and with a significant level (alpha) of 0.05 using a two-sample t-test. For interactions to be detected with the same power as the overall effect, sample sizes should be inflated (Brookes 2004); estimated here at a multiple of fourfold; therefore, to handle potential dropouts, a sample of 1800 patients was considered to be enrolled.

Note that Bayesian inference will be used for sequential analyses, so that no inflation of type I error rate is to be corrected.

Primary outcome

To detect a 10% absolute risk reduction (from 45% to 35%) in the day 90 mortality, a sample size of 373 evaluable patients per arm (thus a total of 746 patients) is required to reach a 80% power. The planned sample of 1800 patients will achieve a 99.16%

power to reject the null hypothesis of equal mortality when the difference between arms is 10% overall, and with a 5% alpha level.

Sample sizes were computed using PASS 15 software (2017).

The power to detect this difference within each group of analysis will depend on the prevalence of each biomarker of interest.

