We will use a Bayesian inference. This is in line with the growing literature to propose Bayesian approaches in randomized clinical trial (), including to identify subpopulations with enhanced treatment effects (Simon 2018). Moreover, it allows to go further than the "statistically significant" findings based on p-values (Wasserstein 2019; Amrhein 2019). Last, Unlike in the frequentist evaluation of the influence condition, the Bayesian evaluation of the influence condition has the advantage of separating the parameters of clinical relevance and risk tolerance (Millen 2014), as detailed below.

Search for treatment-by-cohort interactions will be based on each biomarker and outcome, separately. Treatment-by-covariate interaction will be measured by a Bayesian criterion proposed by Millen (2014), based on the posterior probability of the 'interaction condition' defined in terms of the subpopulation effect sizes estimates:

$P(\hat{\theta}_+/\hat{\theta}_- \geq \lambda_1 | X) \geq \gamma_1,$

where X is the observed data, $\hat{\theta}_+$ is the treatment effect on the efficacy outcome in one subset and $\hat{\theta}_-$ in the remaining subpopulation, λ_1 is a threshold of clinically meaningful effect, close to that proposed by Morita (2014), and γ_1 represents the information threshold for decision-making. Inversely, it will apply to the tolerance outcome, based on

 $P(\hat{t}_+/\hat{t}_- \ge \lambda_2 | X) \ge \gamma_2$, where \hat{t}_+ is the treatment effect on adverse event in one subset and \hat{t}_- in the remaining subpopulation, λ_2 is a threshold of clinically deleterious effect, and γ_2 represents the information threshold for decisionmaking.

The estimates $\hat{\theta}_i$ or $\hat{\tau}_i$ will be defined according to the type of the endpoint, either continuous, with $\hat{\theta}_j$ = $\frac{\hat{\mu}_{Aj} - \hat{\mu}_{Bj}}{\hat{\sigma}_{i}}$, is the effect size defined within each subgroup as the mean treatment

difference divided by the common standard deviation, or binary $\hat{\tau}_j = \frac{\hat{p}_{Aj} - \hat{p}_{Bj}}{|\bar{p}_j(1 - \bar{p}_j)|}$ where \bar{p}_j is the estimated

average adverse event rate.

Noninformative prior distribution will be considered.

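### COVID-19 patients are randomised to a different treatment contrast from the one stated for every biomarker cohort, and section 9 does not set them apart

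*Protocol*

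**What the plan says.** **Stated comparison.** Protocol section 2 says that "several predefined biomarker cohorts of patients will be randomly allocated to receive hydrocortisone plus fludrocortisone or their respective placebos". Section 2.1, which applies to each analysis by biological marker, gives the primary objective as "To compare the effect hydrocortisone plus fludrocortisone vs. placebo on a composite of death or persistent organ dysfunction". Neither makes an exception for COVID-19.

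**COVID-19 patients.** COVID-19 is one of the cohorts in section 4.1.3.1 and one of the nine stratification markers in section 4.5.2. In that cohort "all patients will receive dexamethasone 6 mg per day for 10 days and will be assigned to fludrocortisone or its placebo". The posology section (5.11.4) repeats this: "Patients with COVID-19 will receive only experimental fludrocortisone or its placebo AND NOT hydrocortisone or its placebo".

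**Analysis.** Section 9.2.1 defines two arms, A and B, and gives each subject a set of K biomarkers. It compares the treatment effect in one subset with the effect "in the remaining subpopulation". On power, section 9.1 states: "The planned sample of 1800 patients will achieve a 99.16" per cent, for a difference of 10 points overall between 45% and 35%.

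**Use of the result.** Under section 4.5.1, evidence of harm in a marker group stops its recruitment. It also qualifies the marker as identifying patients who should not be given hydrocortisone plus fludrocortisone.

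**The concern.** The trial contains two randomised contrasts. Outside COVID-19, the arms differ by a glucocorticoid plus a mineralocorticoid. In COVID-19 patients, both arms receive a glucocorticoid and differ only by fludrocortisone. The objectives and section 9 describe only the first.

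Two things are at stake.

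- **The COVID-19 marker.** Section 4.1.3.1 suggests that COVID-19 may identify patients who benefit from corticosteroids. The ratio in section 9.2.1 would set the effect of fludrocortisone on top of dexamethasone in COVID-19 patients against the effect of the combination in everyone else. Marker status and intervention change together, so the ratio cannot separate them. The rule in section 4.5.1 could then draw a conclusion about a combination that was never randomised in this cohort.
- **The other analyses.** If COVID-19 patients stay in the overall comparison and in the subsets of other markers, the estimated effect is a mixture of the two contrasts.

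**Working it through.** **Step 1: the contrasts side by side**

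| Place in the protocol | Who | Randomised difference |
|---|---|---|
| Sections 2 and 2.1 | every biomarker cohort | hydrocortisone + fludrocortisone vs placebos |
| Sections 4.1.3.1 and 5.11.4 | COVID-19 cohort | fludrocortisone vs placebo, all on dexamethasone |
| Section 9.2.1 | all subjects | one A-versus-B effect |

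The first two rows conflict, and the third makes no distinction. This needs no numerical assumption.

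**Step 2: reproduce the protocol's power**

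Inputs from section 9.1: 45% vs 35%, 5% alpha (taken as two-sided), 1800 patients at 1:1, so n = 900 per arm. With the unpooled normal approximation:

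- SE = √[(0.45×0.55 + 0.35×0.65)/900] = 0.02297
- z = 0.10/0.02297 = 4.353
- power = Φ(4.353 − 1.960) = 99.16%

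The same formula gives 372.8, so 373 per arm for 80% power. Both figures in section 9.1 reproduce. (The pooled-variance formula gives the 376 per arm of the study summary.)

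**Step 3: pooling against restriction**

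The protocol gives neither the COVID-19 share c nor the effect of fludrocortisone alone in these patients. Both are assumptions here. Control risk is taken as 45% throughout.

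- Pooled difference = 10×(1 − c) + e×c points, where e is the effect in COVID-19 patients (0 or 5 points), with 900 per arm
- Restricted: a 10-point difference with 900×(1 − c) per arm

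| Share c | Pooled, e = 0: difference, power | Pooled, e = 5: difference, power | Non-COVID-19 only: n per arm, power |
|---|---|---|---|
| 10% | 9.0, 97.4% | 9.5, 98.5% | 810, 98.5% |
| 30% | 7.0, 85.6% | 8.5, 95.8% | 630, 95.4% |
| 50% | 5.0, 57.5% | 7.5, 90.0% | 450, 86.8% |

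Example, c = 30% and e = 0: 45% vs 38%, SE = 0.02317, z = 3.021, power = Φ(3.021 − 1.960) = 85.6%.

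**Step 4: false interaction for another marker**

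The endpoint is vasopressor-free days, with the 3-day effect and SD of 10 from section 9.1. Assumptions: N = 1800, marker prevalence 50%, everyone tested, and no true interaction among non-COVID-19 patients. Each marker level has 450 per arm.

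- SE of the effect in each level = 10×√(2/450) = 0.667
- SE of the difference between levels = 0.667×√2 = 0.943

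| COVID-19 share, marker + vs − | Effect in COVID-19 | Apparent effects (days) | Ratio | Rejection, two-sided 5% |
|---|---|---|---|---|
| 10% vs 10% | 0 | 2.70 vs 2.70 | 1.00 | 5.0% |
| 10% vs 30% | 0 | 2.70 vs 2.10 | 1.29 | 9.8% |
| 10% vs 30% | 1.5 | 2.85 vs 2.55 | 1.12 | 6.2% |
| 10% vs 50% | 0 | 2.70 vs 1.50 | 1.80 | 24.7% |
| 10% vs 50% | 1.5 | 2.85 vs 2.25 | 1.27 | 9.8% |

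These rejection rates are for a conventional interaction test. The posterior-ratio rule in section 9.2.1 depends on thresholds λ and γ, for which the protocol gives no values, so the rate of wrongly closed cohorts cannot be derived from the document.

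**The case against.** A reader might infer that COVID-19 patients are definitely counted in the main comparison and in the subgroups of every other marker. No sentence says so. Section 4.2 assigns a participant to one biomarker cohort, section 9.2.1 searches each cohort separately, and section 4.1.3.1 gives the COVID-19 cohort its own mineralocorticoid question. Section 4.5.2 promises a full statistical analysis plan before the first interim analysis, and that plan may define who belongs to each remainder. This stands: pooling is inferred from the absence of an exclusion.

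A reader might also infer that pooling necessarily dilutes power and creates false interactions. It does not. With half the planned effect in COVID-19 patients, pooling gives slightly more power than restriction at shares of 30% and 50%. Even with zero effect, power at 1800 stays above 80% at a 30% share. With equal COVID-19 shares across marker levels there is no inflation. Moreover, 1800 was derived from the vasopressor-free-days calculation, and 99.16% is stated conditionally on 10 points overall.

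What the objection does not remove is the conflict over the contrast itself. Objectives, randomised treatments and the stated power are fixed in the protocol. An analysis plan can define populations, but it cannot make sections 2 and 2.1 agree with sections 4.1.3.1 and 5.11.4. Nor does a cohort-by-cohort search help the COVID-19 cohort, whose remainder is by definition on the other contrast.

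**Conclusion.** The point holds as a contradiction within the protocol. The contrast stated for every biomarker cohort is not the one to which COVID-19 patients are randomised, no objective covers theirs, and section 9 contains no exclusion. As written, the COVID-19 interaction cannot answer whether COVID-19 status modifies the effect of hydrocortisone plus fludrocortisone. That conclusion rests on no assumption.

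The effect on other analyses is conditional. Power loss requires pooling and a smaller effect in COVID-19 patients. False interactions require, in addition, a COVID-19 share that differs between marker levels. Within the assumed ranges, power at 1800 runs from little changed (98.5% at a 10% share with half effect) to about 57% (50% share, zero effect), and the conventional interaction error from 5% to about 25%. The documents do not support quoting any one of these as the expected result.

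**What to change.** Settle these before the first interim analysis, because interim interaction results can close cohorts:

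1. Reconcile sections 2 and 2.1 with sections 4.1.3.1 and 5.11.4. With the allocation as described in the latter two, state a separate objective and comparison for the COVID-19 cohort: fludrocortisone versus placebo on background dexamethasone, with its own effect size and number.
2. Do not test COVID-19 status as a modifier of the hydrocortisone-plus-fludrocortisone effect, and do not apply the section 4.5.1 conclusion about that combination to this cohort.
3. Define the population for the hydrocortisone-plus-fludrocortisone comparison, and both sides of every other marker's interaction, as non-COVID-19 patients.
4. Restate 99.16% for the expected non-COVID-19 number over a range of shares, for example 98.5%, 95.4% and 86.8% at 10%, 30% and 50%.

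The cost is a smaller number and a lower stated power for the main contrast, plus a sample-size statement for the COVID-19 comparison. Treatment and data collection do not change. If COVID-19 patients had half the planned effect, restriction would gain no power; its gain is an effect estimate that refers to one intervention.

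A separate matter of eligibility wording: interventional exclusion 4, "Formal indication for corticosteroids according to most recent international guidelines", and the enrolment of COVID-19 patients who receive dexamethasone as standard of care (sections 4.1.3.1, 5.11.4 and 5.12) must be reconciled.
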